- 3) Magnetic resonance imaging pathology consistent with clinical symptoms/signs or positive lumbar provocative discography according to SIS/IASP standards at one or two levels.
- 4) Back pain greater than leg pain with an intensity of at least 4/10 or higher using the Numerical Rating Scale (NRS).
- 5) Pain duration of more than 12 weeks despite trial of conservative therapy (medications, physical therapy, or chiropractic care) for 2 months.

Exclusion criteria:

- 1) Refusal to participate, provide consent, or provide follow-up information for the 24-month duration of the study.
- 2) Contraindications to intradiscal injection of PRP (active infection, bleeding disorders, current anticoagulant or antiplatelet medication use, allergy to iodinated contrast, penicillin or clindamycin and pregnancy or breastfeeding).
- 3) More than 2 levels of clinical or discogram proven pain.
- 4) Non-discogenic source of low back pain as identified by separate diagnostic blocks.
- 5) Negative lumbar provocation discography.
- 6) Active moderate to severe lumbar radiculopathy.
- 7) Intradural disc herniation.
- 8) Spinal fracture within the past 6 months.
- 9) Steroid injection in the spine within the last 30 days.
- 10) Any intradiscal injection other than contrast dye or anesthetic in the last 30 days.
- 11) Prior fusion at level considered to be the source of the pain.
- 12) Prior lumbar spine surgery within the last 6 months.
- 13) AP diameter of spinal canal less than or equal to 9mm at level to be treated.
- 14) Severe uncontrolled medical condition.
- 15) Moderate to severe hepatic dysfunction.
- 16) Severe psychological illness.
- 17) History of Inflammatory arthritis.
- 18) Malignancy within past 5 years except basal cell or squamous cell skin cancer.
- 19) Current use of equal to greater than 30mg morphine-equivalent per day of opioid use.
- 20) A history of alcohol or drug abuse within past 5 years.

- 21) Use of any investigational drug within past 30 days.
- 22) A known allergy or sensitivity to citrate (used for processing PRP).
- 23) Severe anaphylactic/anaphylactoid reaction to any medications used.
- 24) Pending litigation involving subject's back pain.
- 25) No insurance coverage for any subsequent tests or procedures.
- 26) Disc protrusion greater than 5mm from base of vertebral body.
- 27) Greater than 50% disc height loss at involved level(s).
- 28) Inability or unwillingness to continue rehabilitation protocols.

Study design:

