Survey/Questionnaire research

Observational research

Prospective Clinical Research

Power Analysis

Size of study groups: 100 total participants.

Procedures:

All visits are standard of care, however completion of questionnaires will be for study purposes in follow-up clinic visits and at specified time-frames. Study involvement includes the following visits:

Screening: Questionnaires and clinical examination

Enrollment: Questionnaire and clinical examination

Follow-up:

- 1 month post-injection- questionnaires and clinical exam
- 2 months post-injection- questionnaire and clinical exam
- 3 months post-injection- questionnaire and clinical exam
- 6 months post-injection- questionnaire and clinical exam
- 9 months post-injection- questionnaire and clinical exam
- 12 months post-injection- questionnaire and clinical exam
- 24 months post-injection- questionnaire and clinical exam
- 36 months post-injection- questionnaire and clinical exam

Questionnaires: Demographics, medication use (MSQ III), ODI, PROMIS PF CAT, PROMIS Global 10, NRS for back and leg pain (current, average last week), PGIC score, PSQ-3, and patient satisfaction with treatment score (5 point: 1, very dissatisfied; 2, dissatisfied; 3, neither satisfied nor dissatisfied; 4, satisfied; and 5, very satisfied).

Data Collection:

An electronic data collection sheet (via iPad) will be used to record all pre-procedure data (see data collection sheet):

- 1) Age (years).
- 2) Sex.
- 3) Height (cm).
- 4) Weight (Kg).
- 5) Duration of pain (weeks).

6) Radiologic diagnosis based on MRI of the Lumbar Spine.
7) NRS for pain; separate scores for back pain and for leg pain

- 8) Oswestry Disability Index (ODI)
- 9) PROMIS Physical Function scale version 2
- 10) PROMIS Global 10
- 11) Medication Quantification Scale (MQS III) score
- 12) Daily opioid use in morphine equivalents

Additional questions for post procedure survey

- 13) Patient Global Impression of Change (PGIC)
- 14) Patient satisfaction score (five-point Likert scale: 1, very dissatisfied; 2, dissatisfied; 3, neither satisfied nor dissatisfied; 4, satisfied; and 5, very satisfied)

Immediately after injection the following will be obtained:

- 15) Fluoroscopy time
- 16) Post-injection NRS pain score; separate scores for back pain and for leg pain
- 17) Adverse events, if they occurred

Data Storage:

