Hard copy data will be collected and stored in a password-protected computer located in the Division of PM&R. Participants will each be assigned an ID number that will be used as the sole identifier on any documents. Participant data will be compiled onto a single password protected file, where they will only be identified by their ID number. An enrollment log will be the only file where subject names are correlated with ID numbers. This will be kept in a separate, secure, password-protected file in the Division of PM&R.

Data Analysis Plan

The primary outcome will be the proportion of participants with >80% and >50% reduction in back pain on the NRS pain score at the 2-month follow-up assessment. Secondary outcomes included reduction in median NRS pain score, ODI, change in PROMIS PF-CAT, MQS III, opioid consumption in daily morphine equivalents, PGIC score, PSQ-3, and satisfaction score. Secondary outcomes will also be defined based on categorical “responder analysis” definitions of important clinical change given the National Institutes of Health recommendation for responder analysis in the assessment of therapeutic spine pain interventions. The responder analysis will include the proportion of patients with 30% or greater improvement on the ODI, a PGIC score less than 3 (indicating “improved” or “very much improved”), a 6.8 or greater point reduction on the MQS III score (equivalent to approximately 10 daily morphine equivalents), and the proportion of participants who undergo surgical spine surgery in the study period.

Statistical analysis

Means and standard deviations of subject demographic data, as well as pain, functional, and treatment satisfaction scores will be calculated. Intergroup differences will be assessed by t test for numerical data and Chi Square or Fisher Exact test for categorical data. Regression modeling will be implemented using ANOVA to assess for patient traits and characteristics that increase the likelihood of efficacy using one technique as opposed to the other.

Risks/Benefits:

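### The one named NRS outcome that is not dichotomised is a reduction in a median, but the statistics section plans means and an intergroup t test, so no within-patient pain change with a confidence interval is planned

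*Combined protocol and SAP*

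**What the plan says.** The Data Analysis Plan makes the primary outcome a responder proportion: "the proportion of participants with >80% and >50% reduction in back pain on the NRS pain score at the 2-month follow-up assessment". Among the secondary outcomes it then lists pain as a reduction in a median: "Secondary outcomes included reduction in median NRS pain score". No visit is attached to that secondary outcome. It does not choose between back and leg pain, or between the current score and the last-week average, although the Procedures section collects all of these.

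The Statistical analysis section says: "Means and standard deviations of subject demographic data, as well as pain, functional, and treatment satisfaction scores will be calculated". For testing it says: "Intergroup differences will be assessed by t test for numerical data". The remaining methods are Chi Square or Fisher tests and ANOVA-based regression. The section mentions no median, quartile, signed-rank test, quantile method, paired analysis or confidence interval.

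The Power Analysis section contains one line, "Size of study groups: 100 total participants", with no SD, correlation, expected change or power.

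**The concern.** The outcome is worded as a median, while every planned summary and test of a numerical score concerns a mean. The named outcome therefore has no method, and the planned method estimates something else. With both in the plan, the choice of summary can be made after the data are seen.

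The planned t test does not close the gap. It compares groups, whereas the documents describe one cohort receiving one intervention and define no comparison group. Change in pain heads the list of objectives, and every patient is meant to have a baseline and follow-up scores. Yet the plan has no estimate of the average change that uses each patient's own baseline and carries an interval.

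A second issue arises if the wording is taken literally. A median before minus a median after discards the pairing, and on a whole-number scale it can take only a few values.

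**Working it through.** **1. The text, side by side.** Outcome: a reduction in a median. Summary: mean and SD. Test: an intergroup comparison of means. None of these yields the named outcome, and none yields a within-patient change with an interval. This step needs no assumption.

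**2. Inputs for the precision check.** From the documents: n = 100, and a baseline NRS of at least 4 out of 10. Assumed, because the documents are silent: SDs, baseline-to-follow-up correlation r, mean change, and whole-number scoring. There is no planned precision figure to reproduce.

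**3. Continuous scores.** For bivariate normal scores with equal SD s:
- Var(mean paired change) = 2s²(1 − r)/n
- Var(difference of medians) = s²(π − 2 arcsin r)/n
- Relative efficiency = 2(1 − r)/(π − 2 arcsin r)

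| r | Efficiency | Patients needed to match 100 analysed by mean change |
|---|---|---|
| 0 | 2/3.142 = 0.64 | 157 |
| 0.3 | 1.4/2.532 = 0.55 | 181 |
| 0.5 | 1/2.094 = 0.48 | 209 |
| 0.7 | 0.6/1.591 = 0.38 | 265 |

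The last column is 100 divided by the unrounded efficiency.

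**4. Whole-number scores.** Simulation at n = 100 used 300 random scenarios: baseline mean 5.5 to 7.5 (SD 1 to 2, scores limited to 4–10), follow-up mean 2.5 to 5.5 (SD 2 to 3, limited to 0–10), r from 0 to 0.7. The efficiency of the difference of medians had median 0.23, 5th to 95th percentile 0.13 to 0.44, minimum 0.09 and maximum 0.78. It was below 1 in every scenario, and also in all 300 scenarios at n = 80.

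The size depends on where the medians fall. With r = 0.5 and SDs of 1.5 at baseline and 2.5 at follow-up:
- Means 6.5 to 4.5 (each between two whole numbers, an unfavourable case): SE 0.594 for the difference of medians against 0.212 for the mean change; efficiency (0.212/0.594)² = 0.13. The estimate was exactly 1, 2 or 3 in (3,084 + 10,755 + 3,224)/20,000 = 85% of simulated trials.
- Means 6.0 to 4.0: SE 0.327 against 0.210; efficiency (0.210/0.327)² = 0.41.

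**5. Coarseness, extreme illustration.** Suppose all 100 patients start at 6. If 49 fall by 5 points, the difference of medians is 0 and the mean change is 49 × 5/100 = 2.45. If 51 do, the difference of medians is 5 and the mean change is 2.55.

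**6. The other reading: median of individual changes.** Efficiency is 2/π = 0.64 under normality. In the 300 whole-number scenarios at n = 100 its median was 0.35, and it beat the mean in about 2% of them.

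**7. What the paired mean would give.** The 95% half-width is 1.96 × SD/√100: 0.39, 0.49 or 0.59 points for an assumed SD of change of 2, 2.5 or 3.

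**The case against.** The strongest reply is that the plan already calls for means and SDs of pain scores. If that section is followed, no precision is lost and what remains is loose wording in one secondary outcome. This stands, and it limits the point. A reader might infer that the trial throws away a large part of its sample, or that the median is its only continuous pain summary. The documents support neither: they do not settle which summary will be reported, and mean pain scores are planned.

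Second, the phrase may loosely mean the median of individual reductions, which does respect pairing. That is a fair reading, and the loss is then usually smaller. The Statistical analysis section does not provide for that quantity either.

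Third, SDs, correlation and whole-number scoring are all assumed, and the lowest efficiencies come from whole-number scoring. The direction held throughout for the difference of medians, but no single effective sample size can be quoted as a property of this trial.

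Fourth, with skewed scores or a mix of responders and non-responders, the mean and the median target different quantities, so an efficiency ratio is then only a rough guide. In one simulated mixture with 30% responders, the median of changes varied less than the mean change. Medians are a legitimate description of bounded, skewed scores. None of this supplies a method for the outcome as named.

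**Conclusion.** The inconsistency is established from the text alone: the one named NRS outcome that is not dichotomised is a median quantity, the planned analysis concerns means, and no within-patient estimate with a confidence interval is planned.

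The loss of precision is conditional. It arises only if a median is the reported estimate. On the literal reading at n = 100, relative efficiency is about 0.4 to 0.6 for continuous scores and roughly 0.13 to 0.6 for whole-number scores, with scenarios outside that range in both directions. All of these figures rest on assumed SDs and correlations. The outcome is secondary and carries no power claim. The primary outcome is already a within-patient percentage reduction and is not touched.

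**What to change.** In the Data Analysis Plan, replace the median phrase with: *mean within-patient change from baseline in back-pain NRS (leg pain separately) at 2 months, with 95% CI (paired)*. State whether the current or the last-week-average NRS is used. Add the paired estimate to the Statistical analysis section, because the intergroup t test does not produce it. Report medians and quartiles at each visit, and of the individual changes, as description.

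The cost is a few lines of text and no new data, since the scores are already collected. There is a small downside: if patients split into responders and non-responders, a mean change may describe few of them. The descriptive medians and the responder-based primary outcome cover that.

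### The plan names no analysis set, longitudinal model or missing-data method for eight visits to 36 months, so later pain and function results are open to attrition bias of unknown direction and size

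*Combined protocol and SAP*

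**What the plan says.** Procedures schedules questionnaires, including NRS, ODI and PROMIS physical function, at 1, 2, 3, 6, 9, 12, 24 and 36 months; the last entry is "36 months post-injection- questionnaire and clinical exam". Visits are described as standard of care, and "completion of questionnaires will be for study purposes in follow-up clinic visits and at specified time-frames". Nothing is said about a missed visit.

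The Data Analysis Plan sets the primary outcome as the proportions passing two thresholds of "reduction in back pain on the NRS pain score at the 2-month follow-up assessment". On the rest it says "Secondary outcomes included reduction in median NRS pain score, ODI, change in PROMIS PF-CAT, MQS III", among others, and it adds responder proportions. It fixes no time point for these secondary outcomes. One of them is "the proportion of participants who undergo surgical spine surgery in the study period", with no rule for pain or function scores recorded after such surgery.

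The Statistical analysis section gives the method: "Means and standard deviations of subject demographic data, as well as pain, functional, and treatment satisfaction scores will be calculated". It continues: "Intergroup differences will be assessed by t test for numerical data and Chi Square or Fisher Exact test for categorical data". A further sentence mentions regression by ANOVA. No section defines an analysis population, a denominator for the responder proportions, a repeated-measures model, a missing-data method or a drop-out allowance.

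Two passages bear on retention. The Exclusion criteria rule out "Refusal to participate, provide consent, or provide follow-up information for the 24-month duration of the study", which falls 12 months short of the last scheduled visit. The Safety Monitoring Plan describes contact in person and by telephone, for safety purposes.

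**The concern.** A mean, a t test or a chi-square test at one visit uses nothing from the earlier visits of a patient who is absent. Unless a rule says otherwise, the summary at each visit is computed on whoever has a score. As patients leave, the set behind the summary changes, and the mean or median can move although no patient has changed.

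Selective loss is plausible here. Questionnaires are tied largely to routine clinic visits, some patients are expected to go on to surgery, and the 36-month visit lies outside the follow-up commitment at entry. A patient without relief may seek care elsewhere; a patient who is well may see no reason to return. These push the result in opposite directions.

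What is at stake is the longer-term result. The Introduction criticises earlier trials for short follow-up, and Risks/Benefits names long-term pain response and function as what the study may clarify. The late visits carry that purpose and are the most exposed to loss.

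**Working it through.** **1. The plan's own figure.** Power Analysis gives 100 participants with no alpha, power, effect size, SD or drop-out allowance. It can be neither reproduced nor refuted, and it supplies no loss rate. Every input below is therefore an assumption.

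**2. Continuous scores.** Let d be the share lost, and mS and mL the mean improvements of stayers and leavers. The full-cohort mean is (1 − d)·mS + d·mL and the attenders' mean is mS, so

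attenders − full cohort = d × (mS − mL).

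| Share lost d | gap 0 | gap 1 | gap 2 | gap 3 |
|---|---|---|---|---|
| 10% | 0 | 0.1 | 0.2 | 0.3 |
| 30% | 0 | 0.3 | 0.6 | 0.9 |
| 50% | 0 | 0.5 | 1.0 | 1.5 |

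Entries are NRS points. A negative gap (leavers improved more) gives the same sizes with the opposite sign.

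**3. Responder proportions.** With true response p and losses dR among improved and dN among unimproved patients,

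observed rate = p(1 − dR) / [p(1 − dR) + (1 − p)(1 − dN)].

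Take 100 patients, p = 50%, improved patients gaining 4 points and the others 0 (true mean 2.00):

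- dR = 10%, dN = 50%: 45/(45 + 25) = 64.3%; mean 4 × 0.643 = 2.57.
- dR = 50%, dN = 10%: 25/(25 + 45) = 35.7%; mean 1.43.
- dR = dN = 20%: 40/80 = 50%; mean 2.00, no bias.

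Counting missing patients as non-responders gives 45%, 25% and 40% in these three cases, all below the true 50%. It is a conservative bound and not a best estimate.

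**4. Simulation over the visit schedule.** Assumptions: baseline NRS mean 6.3, SD 1.3, minimum 4; scores bounded 0-10; patient improvement normal with mean 1.8 and SD 2.0; residual SD 1.2; log-odds of leaving changing by a fixed slope per NRS point at the previous visit, with the stated loss reached by month 36. Slopes of 0.3 to 0.7 mean odds multiplied by about 1.35 to 2 per point. The true mean improvement is about 1.77.

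| Loss by month 36 | Slope | Attenders' mean improvement | Relative to 1.77 |
|---|---|---|---|
| 10% | 0.3 to 0.7 | 1.85-1.93 | +5% to +9% |
| 20% | 0.3 to 0.7 | 1.95-2.08 | +10% to +18% |
| 35% | 0.3 to 0.7 | 2.11-2.32 | +19% to +31% |
| 35% | −0.3 to −0.5 | 1.41-1.23 | −20% to −31% |
| any | 0 | 1.77 | none |

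Step 2 agrees: at 35% loss the implied gaps are (2.11 − 1.77)/0.35 = 0.97 and (2.32 − 1.77)/0.35 = 1.57 points. At 35% loss with positive slopes, response above 50% is 35-38% among attenders against a true 29%.

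These figures use attenders' own change from baseline. If the baseline mean of all patients is set against the month-36 mean of attenders, the apparent improvement at 35% loss is 2.29-2.66, because leavers also had higher baseline pain.

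**5. Does a likelihood model repair it?** With slope 0.5, about 35% loss and leaving driven by the last observed score, an unstructured repeated-measures model gives 1.76 against a true 1.78, so the bias is removed. When leaving is driven by the current, unseen score, the model gives 1.99 against 1.78: 0.21/1.78, about 12% too large. The model corrects only loss that observed scores explain.

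**The case against.** The strongest reply is that the plan does not say what it is charged with. A reader might infer that it prescribes visit-by-visit means in those who attend. The quoted sentence mentions neither visits nor attenders; a mean could be taken over completers or after imputation. That stands: attenders-only summaries are the default when nothing else is stated, not plan text. The defect is the silence.

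A reader might also infer that long-term benefit will be overstated. The documents do not support this. They give no loss rate and no reasons for loss, and with routine-care visits improved patients may be the ones who stop coming, which reverses the bias.

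Nor do the documents tie a secondary result to month 36: no time point is fixed, and the Exclusion criteria put the duration at 24 months. The 35% row is an upper illustration; at 10% loss the effect is under a tenth of the improvement.

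Collection may also be less dependent on attendance than it seems. Questionnaires fall due at specified time-frames as well as at visits, entry requires willingness to give 24 months of information, and telephone contact is mentioned. These may reduce loss, but none is a rule for analysing it.

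Finally, the Statistical analysis section speaks of groups and techniques, while the objective and Procedures read as one injected cohort. If a comparator exists, the drift would cancel only if loss acted equally in both groups, so this does not answer the concern.

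**Conclusion.** The point holds as a gap in the secondary analysis. The stated methods leave the later pain, function and responder results unprotected against loss related to pain, and nothing elsewhere in the document fills the gap. The median NRS reduction is open to the same selection, although its size was not calculated.

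Direction and size are unknown. Under the assumptions shown, the error in mean improvement runs from nothing, through 5-9% at 10% loss, to about 30% either way at 35% loss. The primary outcome, at 2 months, is little affected because little loss has accrued by then, although its denominator is also undefined. A reader should not infer that the primary result is compromised.

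**What to change.** Add to the Statistical analysis section:

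- Change from baseline in back NRS, ODI and PROMIS PF at each visit is estimated by a mixed model for repeated measures using all injected patients and all visits, with baseline in the outcome vector, visit as a category, unstructured covariance and 95% confidence intervals. Nine time points need 9 × 10/2 = 45 covariance parameters from at most 100 patients, so name a simpler structure in advance in case the model does not converge.
- Raw means or medians are shown with the number attending and those patients' own baseline value.
- Responder proportions are reported over all injected patients, with the handling of missing scores stated and missing counted as non-response as a sensitivity analysis.
- A missing-not-at-random sensitivity analysis shifts the missing scores by a pre-specified range of amounts (delta-shift).
- A rule states how scores after spine surgery enter the analysis.

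In Procedures, provide for NRS and ODI by telephone or electronic form when a visit is missed. Settle this early, since scores not collected cannot be recovered. Reconcile the 24-month duration in the Exclusion criteria with the 36-month visit in Procedures.

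The cost is some analysis wording, a standard model, two sensitivity analyses and reminder contacts. The downside is that long-term estimates may move in either direction, with wider intervals.

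### The inferential analysis compares groups and techniques, but the protocol describes one PRP cohort; intervals and a within-patient method for change are not stated

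*Combined protocol and SAP*

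**What the plan says.** The Title, Objectives, Subjects, Procedures and Risks/Benefits sections describe one treatment given to one set of patients. Under Power Analysis the only entry is "Size of study groups: 100 total participants", with no split.

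The Data Analysis Plan section sets the endpoints: "The primary outcome will be the proportion of participants with >80% and >50% reduction in back pain on the NRS pain score", assessed at 2 months. Secondary outcomes include the fall in median NRS, ODI, PROMIS physical function, MQS III and opioid use. There are also responder definitions on ODI, PGIC and MQS III, and the proportion having spine surgery.

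The Statistical analysis section then gives the methods in three sentences:

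- Descriptive: "Means and standard deviations of subject demographic data, as well as pain, functional, and treatment satisfaction scores will be calculated".
- Tests: "Intergroup differences will be assessed by t test for numerical data and Chi Square or Fisher Exact test for categorical data".
- Regression by ANOVA, to "assess for patient traits and characteristics that increase the likelihood of efficacy using one technique as opposed to the other".

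**The concern.** Every inferential method in the Statistical analysis section is comparative, yet the rest of the document gives nothing to compare. The endpoints are of another kind: proportions in one cohort, and changes within the same patients over time. For these the section offers summary statistics only.

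If this stands, whoever runs the analysis must decide what the groups are, how change is assessed and which patients form the denominator of the primary proportions, possibly after seeing the data. The results could then show subgroup P values that do not answer the study's question, with the primary proportions reported without a measure of uncertainty.

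**Working it through.** **1. Design set against analysis**

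| Section | What it describes |
|---|---|
| Title, Objectives | One intervention, intradiscal PRP; outcomes are changes after it |
| Subjects, Power Analysis | 100 participants as a single total |
| Study design, Procedures | Observational and prospective; one schedule with eight follow-up visits (1, 2, 3, 6, 9, 12, 24 and 36 months); no allocation |
| Risks/Benefits | Aim is to understand response after PRP; no data collection is described for patients who decline |
| Statistical analysis | Tests between groups; regression contrasting two techniques |

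The last row has no counterpart in the others. The sample size does not help to identify a second group. The figure of 100 cannot be reproduced, because no significance level, power, effect size, response rate, allocation or dropout is given. That does not make it wrong, but it implies neither one group nor two.

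**2. What the groups could be**

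- *Two techniques.* None is defined, so the technique clause of the regression cannot be carried out.
- *Patient subgroups.* Sex is recorded, and the Inclusion Criteria admit patients on MRI findings or on "positive lumbar provocative discography according to SIS/IASP standards at one or two levels". The t, Chi Square and Fisher tests could be run on such subgroups. They would estimate differences between kinds of patient, not change after injection, and none of these subgroups is a technique.
- *Baseline against follow-up.* This is the right question, but a between-group test ignores that the patients are the same. With equal variance σ² and baseline-to-follow-up correlation ρ, the standard error of the mean difference is √(2σ²/n) if treated as unpaired and √(2σ²(1−ρ)/n) if paired, a ratio of 1/√(1−ρ). For assumed ρ of 0.3, 0.5 and 0.7 the ratio is 1.20, 1.41 and 1.83.

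**3. What an interval would look like**

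For x responders among n, the exact (Clopper-Pearson) 95% limits are the 0.025 quantile of Beta(x, n−x+1) and the 0.975 quantile of Beta(x+1, n−x). The n of 100 comes from the protocol; the response rates are assumed, with no missing data.

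- 50/100: 39.8% to 60.2%, that is 10.2 points either side.
- 20/100: 12.7% to 29.2%, that is 7.3 points below and 9.2 above.

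**4. Why the denominator needs stating**

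Suppose 80 of 100 patients have a 2-month score (assumed) and 40 respond.

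- Of those assessed: 40/80 = 50.0% (38.6% to 61.4%).
- With missing counted as non-response: 40/100 = 40.0% (30.3% to 50.3%).

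The 10-point gap is simply 50.0% × 20/100. It shows how the rule acts and is no forecast for this trial.

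**The case against.** The strongest reply is that the plan says more than it first appears to. It fixes responder cut-offs, several of them percentage or point changes per patient, and names the fall in median NRS. These are within-patient measures, already specified. That stands: a reader might infer that the plan offers nothing beyond means and SDs, and the Data Analysis Plan section does not support that. The gap is narrower: no interval for the proportions, and no paired or repeated-measures method for the continuous scores.

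A second reply is that the intergroup tests are feasible. A reader might infer that none of the comparisons can be run. Only the technique clause is impossible; the intergroup sentence is undefined. The patient-traits part of the regression is usable in one cohort. Efficacy could reasonably be read as the primary outcome, although that outcome has two thresholds and the plan does not say which to model.

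Third, this is observational research with no stated hypothesis about the primary proportion, and a reader could compute an interval from a reported count and denominator. This lowers the weight of the missing interval, but not of the mismatch.

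Finally, entry requires "Back pain greater than leg pain with an intensity of at least 4/10 or higher using the Numerical Rating Scale (NRS" and there is no control, so a reader might add that change cannot be attributed to PRP. That is a limit of the design, separate from this point; the objective is worded as change after injection.

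None of these replies supplies the second technique or identifies the groups.

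**Conclusion.** The concern holds as a mismatch between design and analysis. It rests on the text alone: one cohort and one intervention in the design, but comparisons of unnamed groups and an undefined second technique in the analysis. This must be resolved before analysis.

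The missing interval and the missing denominator rule are lesser omissions that should be fixed. So is the choice of NRS item: current pain and the past-week average are both collected, and the primary outcome does not say which is used.

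The sizes above concern only these omissions. With 100 evaluable patients and assumed response rates of 20% or 50%, the exact limits lie about 7 to 10 points from the estimate. The denominator shift rests on an assumed 20 missing scores. A reader might infer that the primary result is biased by that amount; the documents give no response or dropout rate, so they do not support this. Nor do they show which design was intended.

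**What to change.** Reconcile the design and the Statistical analysis section in a dated amendment before any data are analysed. If a second group or technique was intended, define it and how patients enter it. If the study is a single cohort:

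1. Delete the technique clause. Replace the intergroup sentence, or name the subgroups it refers to and label them exploratory.
2. Report the >50% and >80% NRS responder proportions at 2 months with exact 95% confidence intervals and a stated denominator. One option is all injected patients with missing scores counted as non-response, and a completer analysis as sensitivity. State which NRS item defines response.
3. Analyse change from baseline in the continuous scores with one named within-patient method, for example a repeated-measures mixed model, or a paired test at a named visit.
4. Keep the patient-traits regression, with a named 2-month response outcome.

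For a single cohort the cost is one rewritten paragraph and slightly more analysis, with no extra patients, visits or data. Counting missing scores as non-response lowers the reported rate, which is why the completer analysis is kept beside it. If a second technique was intended, the design section must be rewritten as well.
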